# 11.2 Management of Adverse Events

Adverse events will be collected from the time of signing informed consent form (ICF) through the Follow-up Visit or Early Termination Visit, whichever occurs first.

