6.2 Data Adjustments, Handling, Conventions

All collected data will be presented in listings. Data not subject to analyses according to this plan will not appear in any tables or graphs but will be included only in the data listings.

Adverse events will be coded using the MedDRA (version 19.0). Concomitant and Prior medications will be coded using WHO-DD (version March 1, 2016).

If partial dates occur, the convention for replacing missing dates for the purpose of calculating derived variables is as follows:

For partial start dates:

- If the year is unknown, then do not impute the date but assign a missing value.
- If the month is unknown, then:
 - o If the year matches the year of the randomization date, then impute the month and day of the randomization date.
 - o Otherwise, assign 01 January
- If the day is unknown, then:
 - o If the month and year match the month and year of the randomization date, then impute the day of the first dose date.
 - o Otherwise, assign 01.

For partial end dates:

- If the year is unknown, then do not impute the date but assign a missing value.
- If the month is unknown, then assign the last day of the year 31 December.
- If the day is unknown, then assign the last day of the month.

If an AE has a missing severity, it will be imputed as 'Severe'; any missing relationship to study drug of an AE will be imputed as 'Related'.

SAP FINAL Version 2.0

For the primary endpoint, ADHD-RS-5, missing observations will be imputed by the LOCF method (as described in section 8, below). Other ADHD-RS-5 subscales will impute the value of a missing result if enough data is present (as described in section 6.3).

Page 13 of 88

No other missing data will be imputed.

In general, for quantitative laboratory values reported as '<' or '\(\sigma'\), the lower limit of quantitation (LLOQ) or limit of detection (LOD), one-half of the reported value (i.e., LLOQ, LOD) will be used for analysis.

For quantitative laboratory values reported as '>' or '≥', the upper limit of quantitation (ULOQ), the reported value (i.e., ULOQ) will be used for analysis.

For analysis purposes, repeat laboratory test results will not be used unless the original laboratory value is missing or indicated as invalid, in which case the first non-missing repeat laboratory value will be used for data analysis.

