9.1 Adverse Events

The causal relationship of the AE to the study drug is determined by the investigator as 'not related', 'unlikely/remotely related', 'possibly related', or 'related'. Any AE determined as

SAP FINAL Version 2.0

'possibly related' or 'related' will be considered 'potentially related' to study drug for purposes of analysis of these events.

Page 18 of 88

Missing and partially missing AE start and/or stop dates will be imputed for the purpose of statistical analysis, according to the specifications described in Section 6.2.

Summaries of incidence rates (frequencies and percentages) of individual TEAEs by MedDRA SOC and preferred term will be prepared. Such summaries will be displayed for TEAEs, SAEs, TEAEs leading to early termination, TEAEs by relationship to study drug, TEAEs by severity, TEAEs occurring in more than 5% of subjects, and Post-treatment AEs.

Each patient/subject will be counted only once within each preferred term If a subject experiences more than one TEAE within a preferred term only the TEAE with the strongest relationship or the maximum intensity, as appropriate, will be included in the summaries of relationship and intensity.

Subject listings of all AEs and SAEs, will be presented.

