11.2 Planned Table Shells

Table	Table Title	Topline
14.1.1	Disposition of Study Population by Optimized Dose and Randomized Treatment (ITT Population)	х
14.1.2	Major Protocol Deviations (ITT Population)	
14.1.3	Demographics and Baseline Characteristics by Optimized Dose and Randomized Treatment (Safety Population)	х
14.1.4	Disease Characteristics at Baseline by Optimized Dose and Randomized Treatment (Safety Population)	х
14.1.5	Summary of Prior Medications by Randomized Treatment (Safety Population)	
14.2.1.1	Analysis of Change from Baseline in ADHD-RS-5: Total Score and Subscales, by Study Visit (ITT Population)	х
14.2.1.2	Summary of Change from Baseline in ADHD-RS-5 Score and Subscales by Actual Dose and Randomized Treatment, by Study Visit (ITT Population)	
14.2.2.1	Chi-Square Analysis of CGI-I Improvement, by Study Visit (ITT Population)	х
14.2.2.2	Summary of Categorical and Continuous CGI-I Scores by Randomized Treatment Group and Study Visit (ITT Population)	х
14.2.2.3	Summary of CGI-I Improvement by Optimized Dose and Randomized Treatment, by Study Visit (ITT Population)	
14.2.3.1	Chi-Square Analysis of CGI-S Improvement, by Study Visit (ITT Population)	
14.2.3.2	Summary of Categorical and Continuous CGI-S Scores by Randomized Treatment Group and Study Visit (ITT Population)	
14.2.3.3	Summary of CGI-S Improvement by Optimized Dose and Randomized Treatment, by Study Visit (ITT Population)	
14.2.4.1	Analysis of Change from Baseline in ASHS Total Score and Factors, by Study Visit (ITT Population)	
14.2.4.2	Summary of Change from Baseline in ASHS Total Score and Factors by Randomized Treatment, by Study Visit (ITT Population)	
14.2.5.1	Analysis of Change from Baseline in SCARED Score and Factors, by Study Visit (ITT Population)	
14.2.5.2	Summary of Change from Baseline in SCARED Score and Factors by Randomized Treatment, by Study Visit (ITT Population)	
14.2.6.1	Chi-Square Analysis of Response and Remission Criteria, at End of Study (ITT Population)	х
14.3.1.1	Summary of TEAEs by Dose at Onset (Safety Population)	
14.3.1.2	Incidence of TEAEs by Dose at Onset and Randomized Treatment (Safety Population)	х
14.3.1.3	Incidence of TEAEs occurring in more than 5% of subjects by Randomized Treatment (Safety Population)	

SAP FINAL Version 2.0

14.3.1.4	Incidence of Post-Treatment AE's by Randomized Treatment (Safety Population)	
14.3.1.5	Incidence of SAE's by Randomized Treatment (Safety Population)	

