11.3 Planned Listing Shells

Listing	Listing Title
16.2.1.1	Analysis Populations and Treatment (All Subjects)
16.2.1.2	Subject Disposition (Safety Population)
16.2.1.3	Inclusion/Exclusion Criteria (All Subjects)
16.2.2	Major and Minor Protocol Deviations (Safety Population)
16.2.3.1	Demographics and Other Baseline Characteristics (Safety Population)
16.2.3.2	Prior, Concomitant, and Post-treatment Medications (Safety Population)
16.2.3.3	Behavioral Therapies (Safety Population)
16.2.3.4	Medical History (Safety Population)
16.2.4.1	Study Drug Exposure (Safety Population)
16.2.4.2	Study Drug Accountability and Compliance (Safety Population)
16.2.4.3	Investigator Dose Assessment (Safety Population)
16.2.5.1.1	Attention Deficit Hyperactivity Disorder Rating Scale Version 5 (ADHD-RS-5), part 1 (ITT Population)
16.2.5.1.2	Attention Deficit Hyperactivity Disorder Rating Scale Version 5 (ADHD-RS-5), part 2 (ITT Population)
16.2.5.2	Clinical Global Impression of Improvement (CGI-I) and Clinical Global Impression of Severity (CGI-S) (ITT Population)
16.2.5.3.1	Adolescent Sleep Hygiene Scale (ASHS), part 1 (ITT Population)
16.2.5.3.2	Adolescent Sleep Hygiene Scale (ASHS), part 2 (ITT Population)
16.2.5.3.3	Adolescent Sleep Hygiene Scale (ASHS), part 3 (ITT Population)
16.2.5.3.4	Adolescent Sleep Hygiene Scale (ASHS), part 4 (ITT Population)
16.2.5.4.1	Screen for Childhood Anxiety-related Emotional Disorders (SCARED), part 1 (ITT Population)
16.2.5.4.2	Screen for Childhood Anxiety-related Emotional Disorders (SCARED), part 2 (ITT Population)
16.2.5.4.3	Screen for Childhood Anxiety-related Emotional Disorders (SCARED), part 3 (ITT Population)
16.2.5.4.4	Screen for Childhood Anxiety-related Emotional Disorders (SCARED), part 4 (ITT Population)
16.2.5.5	WASI-II (brief IQ test) (ITT Population)
16.2.5.6.1	Kiddie Schedule for Affective Disorders (K-SADS-PL), part 1 (ITT Population)
16.2.5.6.2	Kiddie Schedule for Affective Disorders (K-SADS-PL), part 2 (ITT Population)
16.2.5.6.3	Kiddie Schedule for Affective Disorders (K-SADS-PL), part 3 (ITT Population)
16.2.5.6.4	Kiddie Schedule for Affective Disorders (K-SADS-PL), part 4 (ITT Population)
16.2.6.1	Adverse Events (Safety Population)
16.2.6.2	Serious Adverse Events (Safety Population)
16.2.6.3	Adverse Events leading to Early Termination (Safety Population)
16.2.6.4	Listing of Deaths (All Subjects)
16.2.7.1	Clinical Laboratory Data: Chemistry (Safety Population)

SAP FINAL Version 2.0

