Note: ADHD-RS-5 = Attention Deficit Hyperactivity Disorder Rating Scale Version 5, CGI-I = Clinical Global Impression of Improvement. Percentages are 100*n/N, where N is the number of non-missing values for corresponding treatment.

Source: Listing 16.2.5.1.1, 16.2.5.1.2, 16.2.5.2

^[1] Response is defined as: (A) a change in ADHD-RS-5 total score from baseline of 30% or more, (B) a CGI-I score of 1 (very much improved) or 2 (much improved) relative to baseline, and (C) a composite requiring both (A) and (B) to be met.

^[2] Remission is defined as: (A) ADHD-RS-5 total score of 18 or less at post-baseline visits, (B) a CGI-I score of 1, and (C) a composite of (A) and (B) to be met

^[3] P-value for comparison of the frequency of Response versus No Response between the NFC-1 and Placebo treatment. The analysis is from a Chi-Square test of association at alpha = 0.05.

Protocol: MDGN-NFC1-ADHD-201

Page 1 of x Final

Table 14.3.1.1 Summary of TEAEs by Dose at Onset Safety Population

Category	NFC-1 100mg (N=xx)	NFC-1 200mg (N=xx)	NFC-1 400mg (N=xx)	All NFC-1 (N=xx)	Placebo (N=xx)
Subjects with at least one:					
Treatment-Emergent Adverse Event	xx (xx x%)	xx (xx x%)	xx (xx.x%)	xx (xx x%)	xx (xx.x%)
TEAE Related to Study Drug [1]	xx (xx x%)	xx (xx x%)	xx (xx.x%)	xx (xx x%)	xx (xx.x%)
Serious Adverse Event	xx (xx x%)	xx (xx x%)	xx (xx.x%)	xx (xx x%)	xx (xx.x%)
TEAE Leading to Study Drug Discontinuation	xx (xx x%)	xx (xx x%)	xx (xx.x%)	xx (xx x%)	xx (xx.x%)
Adverse Event Leading to Death	xx (xx x%)	xx (xx x%)	xx (xx.x%)	xx (xx x%)	xx (xx.x%)

Note: Percentages are 100*n/N. TEAE = Treatment-Emergent Adverse Event

[1] Any AE determined by the investigator as 'possibly related' or 'related' is considered related for purposes of analysis.

Source: Listing 16.2.6.1, 16.2.6.2, 16.2.6.3, 16.2.6.4

Protocol: MDGN-NFC1-ADHD-201

Page 1 of x Final

Table 14.3.1.2
Incidence of TEAEs by Dose at Onset and Randomized Treatment
Safety Population

SOC Preferred Term [1]	NFC-1 100mg (N=xx)	NFC-1 200mg (N=xx)	NFC-1 400mg (N=xx)	NFC-1 (N=xx)	Placebo (N=xx)
Number of Subjects with at Least One AE	xx (xx x%)	xx (xx x%)	xx (xx x%)	xx (xx x%)	xx (xx x%)
<soc 1=""></soc>	xx (xx x%)	xx (xx x%)	xx (xx x%)	xx (xx x%)	xx (xx x%)
<event 1=""></event>	xx (xx x%)	xx (xx x%)	xx (xx x%)	xx (xx x%)	xx (xx x%)
<event 2=""></event>	xx (xx x%)	xx (xx x%)	xx (xx x%)	xx (xx x%)	xx (xx x%)
<event 3=""></event>	xx (xx x%)	xx (xx x%)	xx (xx x%)	xx (xx x%)	xx (xx x%)

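### The AE and SAE listings cover only dosed subjects, so non-fatal wash-out events in never-dosed subjects go unreported, and SAE Table 14.3.1.5 has no onset limit, so it counts pre-dose SAEs under an arm

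*SAP*

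**What the plan says.** Protocol 11.2: "Adverse events will be collected from the time of signing informed consent form (ICF) through the Follow-up Visit" (or the early termination visit, if sooner). Protocol 10.1.1.2 has AEs recorded at the wash-out call, before randomization. Protocol 14.4.2 requires case report forms for everyone who signs consent.

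On listings, SAP 6.2 states "All collected data will be presented in listings", and SAP 9.1 states "Subject listings of all AEs and SAEs, will be presented".

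The index in SAP 11.3 is narrower. Listing 16.2.6.2 is "Serious Adverse Events (Safety Population", and Listing 16.2.6.1 (all AEs) has the same population. SAP 5 defines that population as subjects randomized and given any amount of product. Listing 16.2.6.4 (deaths) covers all subjects. Disposition Listing 16.2.1.2 is "Subject Disposition (Safety Population", and deviation Listing 16.2.2 has the same limit.

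On tables, Table 14.3.1.5 is "Incidence of SAE's by Randomized Treatment (Safety Population". Its shell asks only for a footnote defining an SAE and a new first row. Table 14.3.1.1 is titled "Summary of TEAEs by Dose at Onset" but contains a row for serious adverse events with no treatment-emergent qualifier.

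**The concern.** The same kind of event is handled in two unsatisfactory ways, depending on whether the subject goes on to be dosed.

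If the subject is dosed, an SAE that began during screening or wash-out enters the between-arm SAE table as though it belonged to the assigned treatment. Serious events are likely to be few in a six-week study of about 90 adolescents, so one misplaced event is visible in that comparison.

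If the subject is never dosed, a non-fatal event has no place in the AE or SAE outputs. For some subjects this period includes withdrawal of ADHD medication required by the protocol, so these events bear on the safety of the study procedures. There is no data safety monitoring board (Protocol 12), so the final outputs are the main place where such events would be seen together.

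**Working it through.** No figure in the plan has to be reproduced. The check sets the collection window, definitions, populations and output specifications side by side.

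**Definitions**

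1. Collection window: from consent (Protocol 11.2). Protocol 10.2 allows up to 21 days of screening, including at most 14 days of wash-out, then about 42 days of treatment and 7 of follow-up.
2. Treatment-emergent: first onset or worsening after the first dose and no more than 7 days after the last (SAP 6.3). An event confined to wash-out is not treatment-emergent.
3. Post-treatment AE: onset more than 7 days after the last dose (SAP 6.3).

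**Is the SAE summary limited to treatment-emergent events?** SAP 9.1 names TEAEs, then SAEs without the qualifier, then further TEAE summaries, then post-treatment AEs. The whole list cannot be read as treatment-emergent only, because post-treatment AEs fall outside that window by definition. Protocol 13.4.4.1 also names SAEs without a limit. Neither the title nor the shell of Table 14.3.1.5 adds one. On the plain wording, any SAE in a dosed subject is counted.

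**Where a wash-out SAE goes**

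- Subject later dosed: counted under the randomized arm in Table 14.3.1.5, and listed in 16.2.6.1 and 16.2.6.2 with the TEAE column set to No.
- Subject never dosed, event not fatal: in no AE or SAE table and in neither listing.
- Subject never dosed, event fatal: in Listing 16.2.6.4.

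A non-fatal, non-serious wash-out AE in a never-dosed subject is lost in the same way as in the second case.

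**Table 14.3.1.1.** Its title confines it to TEAEs by dose at onset, and a pre-dose event has no dose at onset. Its SAE row is unqualified, as is its row for events leading to death, while the other three rows are treatment-emergent. The shell supports either reading.

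**Source listings.** Table 14.1.1 is an ITT table with rows for screened subjects and screen failures, yet it cites Listing 16.2.1.2 as its source. Table 14.1.2 is an ITT table and cites Listing 16.2.2. Both listings omit randomized-but-undosed subjects, and Listing 16.2.1.2 also omits the screen failures. SAP 7.1 says that every consenting subject will be accounted for and that disposition information will be listed in full.

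**Scale**

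- Pre-dose share of the scheduled observation time for a dosed subject: 21 / (21 + 42 + 7) = 21/70 = 30%, taking the full 21 days.
- Effect of one pre-dose SAE on an arm's incidence, with about 45 subjects per arm (Protocol 7.1): 1/45 = 2.2 percentage points.

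**The case against.** Counting every SAE in dosed subjects is a recognized, inclusive choice and follows Protocol 13.4.4.1. Limiting Table 14.3.1.5 to treatment-emergent SAEs would do harm: the follow-up call may fall up to 5 days after Day 49, and an SAE starting more than 7 days after the last dose would leave the SAE tables, remaining only in Table 14.3.1.4 without being identified as serious. This stands. The remedy is to separate the periods, not to discard events.

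The AE listing shell already has a TEAE column and start times, with a sample row that is serious but not treatment-emergent. The SAE listing copies that shell. A pre-dose SAE in a dosed subject can therefore be identified in the listing. This stands too, but it does not help a reader of the table and does nothing for undosed subjects.

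Pre-dose events are balanced between arms in expectation, no formal safety inference is planned (Protocol 13.4.4), and a subject with a wash-out SAE must still pass the baseline eligibility review. All true, and they limit the consequence. With few events, however, balance in expectation does not prevent imbalance in the table actually seen.

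SAEs are reported within 24 hours in any case, and Appendix A may be updated independently of the SAP. The first does not put the events into the study outputs. The second makes correction easy.

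**Conclusion.** The point holds for non-fatal AEs and SAEs in never-dosed subjects. Following the shells as written breaks the promises in SAP 6.2 and 9.1. It also holds for Table 14.3.1.5, which attributes pre-dose SAEs in dosed subjects to an arm at 2.2 percentage points per affected subject, assuming 45 dosed per arm. The mismatch between Listings 16.2.1.2 and 16.2.2 and the ITT tables they source is a separate, smaller inconsistency.

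Three stronger readings are tempting and are not supported:

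- A reader might infer that an event in an undosed subject appears in no output at all. Deaths are listed for all subjects, and a randomized-but-undosed subject who stops because of an AE is counted, as a reason only, in Table 14.1.1.
- A reader might infer that Table 14.3.1.1 definitely counts pre-dose SAEs. Its title points the other way; the row is ambiguous, not plainly wrong.
- A reader might try to state what share of events or observation time goes unlisted. The documents give neither the proportion failing before dosing nor how long such subjects are observed, so no such figure is offered.

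The efficacy analysis is not affected. The correction is worth making before database lock because it is nearly free.

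**What to change.** 1. Set Listings 16.2.6.1 and 16.2.6.2 to All Subjects, defined as all who signed consent, and extend the existing TEAE column to three values: pre-treatment, treatment-emergent, post-treatment.
2. In Table 14.3.1.5, show treatment-emergent SAEs by arm, with pre-treatment and post-treatment SAEs in separate rows so that none is lost.
3. In Table 14.3.1.1, label the row *Treatment-Emergent Serious Adverse Event*.
4. Set Listings 16.2.1.2 and 16.2.2 to All Subjects so that they support Tables 14.1.1 and 14.1.2.

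This changes titles, row labels and a population filter in Appendix A. It needs no new data, and Listings 16.2.1.1, 16.2.1.3 and 16.2.6.4 already use All Subjects. The cost is slightly longer listings and extra rows in one table.

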<medication 2=""></medication>	xx (xx x%)	xx (xx x%)	xx (xx.x%)
<medication 3=""></medication>	xx (xx x%)	xx (xx x%)	xx (xx.x%)
<atc 3=""></atc>	xx (xx x%)	xx (xx x%)	xx (xx.x%)
<medication 1=""></medication>	xx (xx x%)	xx (xx x%)	xx (xx.x%)
<medication 2=""></medication>	xx (xx x%)	xx (xx x%)	xx (xx.x%)
<medication 3=""></medication>	xx (xx x%)	xx (xx x%)	xx (xx.x%)

Note: Percentages are 100*n/N. Subjects were counted only once for each Anatomical Therapeutic Chemical (ATC) or Preferred Term. Concomitant medications are defined as any medication a subject received concurrently with study treatment.

Source: Listing 16.2.3.2

^[1] Medications were coded using WHO-DD (Enhanced version xxxx) ATC Level 3.

Table 14.3.8 Summary of Post-Treatment Medications by Randomized Treatment Safety Population

{Similar shell as Table 14.3.7; Source: Listing 16.2.3.2} {Update footnote and first row label accordingly}

Page 1 of x Final

Listing 16.2.1.1 Analysis Populations and Treatment All Subjects

		Treatment	Treatment	Randomization	Reason Excluded	An	alysis Popu	ılation
Subject ID	Treatment	Start Date	End Date	Number	From Population	Safety	ITT	Per-Protocol
xxxxxxx	NFC-1	DDMMYYYY	DDMMYYYY	XXXXX	xxxxxxxxxx	Yes	Yes	No
xxxxxxx	NFC-1	DDMMYYYY	DDMMYYYY	XXXXX		Yes	Yes	Yes
xxxxxxx	Placebo	DDMMYYYY	DDMMYYYY	XXXXX	xxxxxxxxxxx; xxxxxxxx	No	Yes	No
xxxxxxxx	NFC-1	DDMMYYYY	DDMMYYYY	XXXXX	xxxxxx; xxxxxxxxx; xxxxx	No	No	No

Protocol: MDGN-NFC1-ADHD-201

Page 1 of x Final

Listing 16.2.1.2 Subject Disposition Safety Population

Subject ID	Treatment	Completed Study?	Follow-up Phone Call?	Date of Discontinuation	Reason for Discontinuation	Date of Last Contact
xxxxxxx	NFC-1	Yes	Yes			DDMMYYYY
xxxxxxx	NFC-1	Yes	Yes			DDMMYYYY
xxxxxxx	Placebo	No	No	DDMMYYYY	xxxxxxxxxx	DDMMYYYY
xxxxxxxx	NFC-1	No	No	DDMMYYYY	Other; xxxxxxx xxxxxxx	DDMMYYYY

T:\Medgenics\NFC-1\ADHD-201\...\xxx.sas run on DDMMMYYYY at HH:MM on data extracted on DDMMMYYYY

{If subject discontinued due to reason = 'Other', concatenate discontinuation reason field with Other with a ';', as per the example above}

Page 1 of x Final

Listing 16.2.1.3 Inclusion/Exclusion Criteria All Subjects

Treatment: XXXXX

Subject ID	Were all Inclusion Criteria Met?	Category Not Met	Criteria Not Met
xxxxxxx	No	Inclusion	INCL01; INCL04; INCL10
xxxxxxx	Yes		
xxxxxxx	Yes		
xxxxxxx	No	Inclusion; Exclusion	INCL02; INCL03; EXCL15; EXCL18G

Page 1 of x Final

Listing 16.2.2 Major and Minor Protocol Deviations Safety Population

Treatment: XXXXX

Subject ID	Event Date	Event Report Date	Event Category	Event Type	Description
xxxxxxxx	DDMMYYYY DDMMYYYY DDMMYYYY	DDMMYYYY DDMMYYYY DDMMYYYY	Major Major Minor	Informed Consent/Assent Concomitant Medication Other	xxxxxxxxxxxxxxxxxxxxxxxxxxxxxxxxxxxxxx
xxxxxxxx	DDMMYYYY DDMMYYYY	DDMMYYYY DDMMYYYY	Minor Minor	Study Assessments/Procedures Inclusion/Exclusion Criteria	xxxxxxxxxx xxxxxxxxxxxxxxxxxxxxxxxxxxx
XXXXXXX	DDMMYYYY DDMMYYYY	DDMMYYYY DDMMYYYY	Major Major	Laboratory Assessment Laboratory Assessment	xxxxxxxxxxxxxxxxxxxxxxxxxxxxxxxxxxxxxx
xxxxxxx	DDMMYYYY	DDMMYYYY	Major	Other	xxxxxxxxxxxxxxxxxxxxxxxxxxxxxxxxxxxxxx

Protocol: MDGN-NFC1-ADHD-201

Page 1 of x Final

Listing 16.2.3.1 Demographics and Other Baseline Characteristics Safety Population

Treatment: XXXXXX

Subject ID	Previous Subject ID from ADHD-001	Date of Parental Informed Consent	Date of Informed Assent	Date of Birth	Age (yrs)/ Gender	СВ	Ethnicity	Race	ADHD Diagnosis Date (Age at Onset) (yrs)
xxxxxxxx	xxxxxxx	DDMMYYYY	DDMMYYYY	DDMMYYYY	xx/F	No	xxxxxxxxx	White	DDMMYYYY (13)
xxxxxxxx	xxxxxxxx	DDMMYYYY	DDMMYYYY	DDMMYYYY	xx/M	No	xxxxx	Asian	DDMMYYYY (8)
xxxxxxx	xxxxxxxx	DDMMYYYY	DDMMYYYY	DDMMYYYY	xx/F	Yes	xxxxxxxxxx	White	DDMMYYYY (10)
xxxxxxx	xxxxxxx	DDMMYYYY	DDMMYYYY	DDMMYYYY	xx/F	Yes	xxxxxxxxxx	Black or African American	DDMMYYYY (14)

Note: NA = not applicable. yrs = Years. CB = If Female, is She of Childbearing Potential.

Protocol: MDGN-NFC1-ADHD-201

Page 1 of x Final

Listing 16.2.3.2 Prior, Concomitant, and Post-treatment Medications Safety Population

Treatment: XXXXXX

			Anatomic Therapeutic Class/			Dose (unit)/
	Any	Concomitant/	Preferred Term/	Start Date/		Route/
Subject ID	Meds?	Prior/Both	Verbatim Term	End Date	Indication	Frequency
			xxxxxxxxxxxxxxxxxx/			xxxx (xxxx)/
			xxxxxxxxxxxxxxx/	DDMMYYY/		xxxxxxxxx/
xxxxxxx	Yes	P	xxxxxxxxxxxxxxxxxx	DDMMYYY	xxxxxxxxxxx	XXXXXXXXXX
			xxxxxxxxxxxxxxxxxxxxxxxxxxxx/			xxxx (xxxx)/
			xxxxxxxxxx/	DDMMYYY/		xxxxxxxxx/
		P	xxxxxxxxxxxxxxx	ONGOING	xxxxxxxxxxx	xxxxxxxxxx
			xxxxxxxxxxxxxxxxxxxxxxxxxxxx/			xxxx (xxxx)/
			xxxxxxxxxxxxxxxx/	DDMMYYY/		xxxxxxxxx/
		C	xxxxxxxxxx	DDMMYYY	xxxxxxxxxxx	xxxxxxxxxx
			xxxxxxxxxxxxxxxxxxx/			xxxx (xxxx)/
			xxxxxxxxxxxxxxxx/	DDMMYYY/		xxxxxxxxx/
xxxxxxx	Yes	В	xxxxxxxxxxx	DDMMYYY	xxxxxxxxxxx	XXXXXXXXXX
			xxxxxxxxxxxxxxxxxxxxxxxxxxx/			xxxx (xxxx)/
			xxxxxxxxxx/	DDMMYYY/		xxxxxxxxx/
		В	XXXXXXXXXXXXXXXX	DDMMYYY	xxxxxxxxxxx	XXXXXXXXXX

Note: Medications were coded using WHO-DD (Enhanced version xxxxxx), Anatomic Therapeutic Class (ATC), level 4. B = Both, C = Concomitant, P = Prior. T:\Medgenics\NFC-1\ADHD-201\...\xxx.sas run on DDMMMYYYY at HH:MM on data extracted on DDMMMYYYY

CONFIDENTIAL AD-ST-33.03 16 Mar 2012

Page 1 of x Final

Listing 16.2.3.3 Behavioral Therapies Safety Population

Subject ID	Any Therapies?	Type of Therapy	Start Date/ End Date	Frequency
xxxxxxx	Yes	xxxxxxxxxxx	DDMMYYY/ DDMMYYY	XXXXXXXXXX
		xxxxxxxxxxxxxx	DDMMYYY/ ONGOING	xxxxxxxxxxxxx
		xxxxxxxxxxx	DDMMYYY/ DDMMYYY	xxxxxxxxxxxx
xxxxxxx	Yes	xxxxxxxxxxx	DDMMYYY/ DDMMYYY	xxxxxxxxxx
		xxxxxxxxxxxxx	DDMMYYY/ DDMMYYY	XXXXXXXXXXXXXX

T:\Medgenics\NFC-1\ADHD-201\...\xxx.sas run on DDMMMYYYY at HH:MM on data extracted on DDMMMYYYY

Page 1 of x Final

Listing 16.2.3.4 Medical History Safety Population

Subject ID	Any History?	Verbatim Term	Start Date/ End Date
xxxxxxx	Yes	xxxxxxxxxxxxxxxxxxxxxxxx	DDMMYYY/ DDMMYYY
		xxxxxxxxxxxxxxxxxx	DDMMYYY/ ONGOING
		XXXXXXXXXXXX	DDMMYYY/ DDMMYYY
xxxxxxx	Yes	xxxxxxxxxxxxxxx	DDMMYYY/ DDMMYYY
		xxxxxxxxxxxxxxxxxxxxxxxx	DDMMYYY/ DDMMYYY

T:\Medgenics\NFC-1\ADHD-201\...\xxx.sas run on DDMMMYYYY at HH:MM on data extracted on DDMMMYYYY

Protocol: MDGN-NFC1-ADHD-201

Page 1 of x Final

Listing 16.2.4.1 Study Drug Exposure Safety Population

Subject ID	Dose (mg)	Start Date (Study Day) [1]	End Date (Study Day) [1]	Treatment Duration (days) [2]
Subject ID	Dosc (mg)	(Study Day) [1]	(Study Day) [1]	Treatment Duration (days) [2]
xxxxxxx	XXX	DDMMYYYY	DDMMYYYY	X
	XXX	DDMMYYYY	DDMMYYYY	X
	XXX	DDMMYYYY	DDMMYYYY	XX
	XXX	DDMMYYYY	DDMMYYYY	XX
	XXX	DDMMYYYY	DDMMYYYY	XX
xxxxxxx	XXX	DDMMYYYY	DDMMYYYY	X
	XXX	DDMMYYYY	DDMMYYYY	X
	XXX	DDMMYYYY	DDMMYYYY	XX
	XXX	DDMMYYYY	DDMMYYYY	XX
	XXX	DDMMYYYY	DDMMYYYY	XX
xxxxxxxx	XXX	DDMMYYYY	DDMMYYYY	X
	XXX	DDMMYYYY	DDMMYYYY	X
	XXX	DDMMYYYY	DDMMYYYY	XX
xxxxxxx	XXX	DDMMYYYY	DDMMYYYY	X
	XXX	DDMMYYYY	DDMMYYYY	X
	XXX	DDMMYYYY	DDMMYYYY	XX
	XXX	DDMMYYYY	DDMMYYYY	XX
	XXX	DDMMYYYY	DDMMYYYY	XX

^[1] Study Day is calculated relative to the date of the first dose of study drug.

^[2] Treatment Duration is defined as Date of Last Dose – Date of First Dose + 1 for the specified Dose level.

T:\Medgenics\NFC-1\ADHD-201\...\xxx.sas run on DDMMMYYYY at HH:MM on data extracted on DDMMMYYYY

Protocol: MDGN-NFC1-ADHD-201

Page 1 of x Final

Listing 16.2.4.2
Study Drug Accountability and Compliance
Safety Population

Subject ID			Date Bottle	Date Bottle Returned	Capsules — Returned	Compliance [1]	
	Visit		Dispensed			By Week	Overall
xxxxxxx	Visit 3	XX	DDMMYYYY			xx x%	
	Visit 4					xx x%	
	Visit 5					xx x%	
	Visit 6			DDMMYYYY	XX	xx x%	xx x%
xxxxxxx	Visit 3	XX	DDMMYYYY			xx x%	
	Visit 4		22			XX X%	
	Visit 5					xx x%	
	Visit 6			DDMMYYYY	XX	XX X%	
	Visit 7					XX X%	
	Visit 8/ET			DDMMYYYY	XX	xx x%	xx x%

^[1] A subject is non-compliant if they take < 80% or > 100% of IP. Compliance (Overall) = (sum of (Individual Week Compliance) * (Time-Weight)) * 100. Individual Week Compliance is defined as the number of capsules taken at a particular week divided by the expected number of capsules taken at a particular week. Given that a subject will be dose optimized, the number of expected capsules will vary according to which dose the subject is currently on for each day. Time-Weight is the fraction of x/y where x is the number of days in the week the subject is expected to be on dose and is the whole treatment duration.

T:\Medgenics\NFC-1\ADHD-201\...\xxx.sas run on DDMMMYYYY at HH:MM on data extracted on DDMMMYYYY

Medgenics, Inc. Protocol: MDGN-NFC1-ADHD-201

Page 1 of x Final

Listing 16.2.4.3 Investigator Dose Optimization Safety Population

Treatment: XXXXXX

		Investigator			
		Assess Efficacy	Date of Dose	Response	Dose Optimization -
Subject ID	Dose (mg)	of Current Dose?	Assessment	Categorization	Action Taken
XXXXXXXX	XXX	Yes	DDMMYYYY	Acceptable	DOSE INCREASED
	XXX	Yes	DDMMYYYY	Acceptable	DOSE INCREASED
	XXX	Yes	DDMMYYYY	Acceptable	DOSE INCREASED
	XXX	No			
	XXX	Yes	DDMMYYYY	Acceptable	DOSE MAINTAINEI
xxxxxxx	xxx	Yes	DDMMYYYY	Acceptable	DOSE INCREASED
	XXX	Yes	DDMMYYYY	Acceptable	DOSE INCREASED
	XXX	Yes	DDMMYYYY	Acceptable	DOSE INCREASED
	XXX	No		•	
	XXX	Yes	DDMMYYYY	Acceptable	DOSE MAINTAINE
xxxxxxx	XXX	Yes	DDMMYYYY	Acceptable	DOSE INCREASED
	XXX	Yes	DDMMYYYY	Acceptable	DOSE INCREASED
	xxx	Yes	DDMMYYYY	Ineffective	DOSE MAINTAINE
xxxxxxx	XXX	Yes	DDMMYYYY	Acceptable	DOSE INCREASED
	XXX	Yes	DDMMYYYY	Acceptable	DOSE INCREASED
	XXX	Yes	DDMMYYYY	Acceptable	DOSE INCREASED
	XXX	Yes	DDMMYYYY	Ineffective	DOSE DECREASEI
	XXX	Yes	DDMMYYYY	Intolerable	IP DISCONTINUEI

T:\Medgenics\NFC-1\ADHD-201\...\xxx.sas run on DDMMMYYYY at HH:MM on data extracted on DDMMMYYYY

Protocol: MDGN-NFC1-ADHD-201

Page 1 of x Final

Listing 16.2.5.1.1
Attention Deficit Hyperactivity Disorder Rating Scale Version 5 (ADHD-RS-5), part 1
Intent-To-Treat Population

Treatment: XXXXXX

Subject ID	Visit	Performed?	Date Performed	Q4	Q5	Q6	Q7	Q8	Q9	Q10	Q11	Q12	Q13	Q14	Q15	Q16	Q17	Q18	Q19	Q20
xxxxxxxx	Screening	Yes	DDMMYYYY	Y	Y	Y	Y	N	Y	Y	N	Y	0	0	0	0	0	0	1	2
	Baseline	Yes	DDMMYYYY	Y	Y	Y	Y	N	Y	Y	N	Y	1	0	0	1	0	0	3	1
	Visit 3	Yes	DDMMYYYY	Y	Y	Y	Y	N	Y	Y	N	N	0	0	0	0	0	0	1	2
	Visit 4	Yes	DDMMYYYY	Y	Y	Y	Y	N	Y	Y	N	N	1	0	0	1	0	0	3	1
	Visit 5	No																		
	Visit 6	Yes	DDMMYYYY	Y	Y	Y	Y	Y	Y	Y	N	N	0	0	0	0	0	0	1	2
	Visit 7	Yes	DDMMYYYY	Y	Y	Y	Y	Y	Y	Y	N	Y	1	0	0	1	0	0	3	1
	Visit 8/ET	Yes	DDMMYYYY	Y	Y	Y	Y	N	Y	Y	N	N	1	0	0	1	0	0	3	1

Note: Y = Yes, N = No. For Questions 13 - 18: 0 - Never or Rarely, 1 - Sometimes, 2 - Often, 3 - Very often. For Questions 19-33: 0 - No problem, 1 - Minor problem, 2 - Moderate Problem, 3 - Severe Problem

T:\Medgenics\NFC-1\ADHD-201\...\xxx.sas run on DDMMMYYYY at HH:MM on data extracted on DDMMMYYYY

Listing 16.2.5.1.2
Attention Deficit Hyperactivity Disorder Rating Scale Version 5 (ADHD-RS-5), part 2
Intent-To-Treat Population

{Similar shell as Listing 16.2.5.1.1, using Questions 21 – 33 and Inattention Subscale, Hyperactivity/Impulsivity Subscale, and ADHD RS-5 Total Score}

Protocol: MDGN-NFC1-ADHD-201

Page 1 of x Final

Listing 16.2.5.2
Clinical Global Impression of Improvement (CGI-I) and Clinical Global Impression of Severity (CGI-S)
Intent-To-Treat Population

Treatment: X	XXXXX				
Subject ID	Visit	Performed CGI-I/ Performed CGI-S	Date Performed	CGI-I	CGI-S
xxxxxxx	Screening Baseline	NA/Yes NA/Yes	DDMMYYYY DDMMYYYY		Normal, not at all ill Borderline mentally ill
	Visit 3 Visit 4	Yes/NA Yes/NA	DDMMYYYY DDMMYYYY	No change Minimally worse	Borderinie mentany m
	Visit 5 Visit 6	Yes/NA Yes/NA	DDMMYYYY DDMMYYYY	Minimally improved Much improved	
	Visit 7 Visit 8/ET	Yes/NA Yes/Yes	DDMMYYYY DDMMYYYY	Much improved Very much Improved	Normal, not at all ill

T:\Medgenics\NFC-1\ADHD-201\...\xxx.sas run on DDMMMYYYY at HH:MM on data extracted on DDMMMYYYY

Listing 16.2.5.3.1 Adolescent Sleep Hygiene Scale (ASHS), part 1 Intent-To-Treat Population

{Similar shell as Listing 16.2.5.1.1} {Include questions 4-15, add footnote regarding decode values, see eCRF}

Listing 16.2.5.3.2

Adolescent Sleep Hygiene Scale (ASHS), part 2

Intent-To-Treat Population

{Similar shell as Listing 16.2.5.1.1} {Include questions 16-25, add footnote regarding decode values, see eCRF}

Listing 16.2.5.3.3
Adolescent Sleep Hygiene Scale (ASHS), part 3
Intent-To-Treat Population

{Similar shell as Listing 16.2.5.1.1} {Include questions 26-40, add footnote regarding decode values, see eCRF}

Listing 16.2.5.3.4 Adolescent Sleep Hygiene Scale (ASHS), part 4 Intent-To-Treat Population

{Similar shell as Listing 16.2.5.1.1} {Include factors for ASHS and total score, add footnote regarding decode values, see eCRF}

Listing 16.2.5.4.1 Screen for Childhood Anxiety-related Emotional Disorders (SCARED), part 1 Intent-To-Treat Population

{Similar shell as Listing 16.2.5.1.1} {Include questions 1-15, add footnote regarding decode values, see eCRF}

Listing 16.2.5.4.2 Screen for Childhood Anxiety-related Emotional Disorders (SCARED), part 2 Intent-To-Treat Population

{Similar shell as Listing 16.2.5.1.1} {Include questions 16-25, add footnote regarding decode values, see eCRF}

Listing 16.2.5.4.3

Screen for Childhood Anxiety-related Emotional Disorders (SCARED), part 3
Intent-To-Treat Population

{Similar shell as Listing 16.2.5.1.1}

{Include questions 26-41, add footnote regarding decode values, see eCRF}

Listing 16.2.5.4.4

Screen for Childhood Anxiety-related Emotional Disorders (SCARED), part 4
Intent-To-Treat Population

{Similar shell as Listing 16.2.5.1.1}

{Include factors for SCARED and total score, add footnote regarding decode values, see eCRF}

Listing 16.2.5.5 WASI-II (brief IQ test) Intent-To-Treat Population

{Similar shell as Listing 16.2.5.1.1}

Listing 16.2.5.6.1 Kiddie Schedule for Affective Disorders (K-SADS-PL), part 1 Intent-To-Treat Population

{Similar shell as Listing 16.2.5.1.1, {Include questions 4-20, add footnote regarding decode values, see eCRF}

Listing 16.2.5.6.2 Kiddie Schedule for Affective Disorders (K-SADS-PL), part 2 Intent-To-Treat Population

{Similar shell as Listing 16.2.5.1.1, {Include questions 21-37, add footnote regarding decode values, see eCRF}

Listing 16.2.5.6.3 Kiddie Schedule for Affective Disorders (K-SADS-PL), part 3 Intent-To-Treat Population

{Similar shell as Listing 16.2.5.1.1, {Include questions 38-55, add footnote regarding decode values, see eCRF}

Listing 16.2.5.6.4 Kiddie Schedule for Affective Disorders (K-SADS-PL), part 4 Intent-To-Treat Population

{Similar shell as Listing 16.2.5.1.1, {Include questions 56-60, add footnote regarding decode values, see eCRF}

Protocol: MDGN-NFC1-ADHD-201

Page 1 of x Final

Listing 16.2.6.1 Adverse Events Safety Population

Treatment: XXXXXX

		System Organ Class/				Outcome/		
	Any	Preferred Term/		Start Datetime/	Severity/	Study Drug		IME/CA/SD/
Subject ID	AEs?	Verbatim Term	TEAE?	End Datetime	Relationship to IP	Action Taken	SE	DE/HO/LT/
xxxxxxx	Yes	xxxxxxxxxxxx/ xxxxxxxxxxxxxxxxxx/ xxxxxx	Yes	DDMMYYY:HH:MM/ DDMMYYY:HH:MM	xxxxxxxx/ xxxxxx	xxxxxxxx/ xxxxxx xxxxx	No	No/No/No No/No/No
		xxxxxxxxxxxxxx/ xxxxxxxxxxxxxxxxxxxxxx	Yes	DDMMYYY:HH:MM / ONGOING	xxxxxxx/ xxxx	xxxxxxx/ xxxxxxxxxx	No	No/No/No No/No/No
		xxxxxxxxxxxxxxxxxxxxxxxxxxxxxxxxxxxxxx	No	DDMMYYY:HH:MM/ DDMMYYY:HH:MM	xxxxxxxx/ xxxxx	xxxxxxx/ xxxxxxxxxxx	Yes	Yes/Yes/No/ Yes/No/No
xxxxxxx	Yes	xxxxxxxxxxxx/ xxxxxxxxxxxxxxx/ xxxxxxxx	Yes	DDMMYYY:HH:MM/ DDMMYYY:HH:MM	xxxxxx/ xxxx	xxxxxx/ xxxxxxxx	Yes	No/No/No/ Yes/No/No
		xxxxxxxxxxxxxxxxxxxxxxxxxxxx/ xxxxxxxxx	Yes	DDMMYYY:HH:MM/ DDMMYYY:HH:MM	xxxxxxx/ xxxxx	xxxxxx/ xxxxx	No	No/No/No No/No/No

Note: Adverse Events were coded using MedDRA version xx x. CA = Congenital Anomaly; DE = Results in Death; HO = Hospitalization; IME = Important Medical Event; IP = Investigational Product; LT = Life Threatening; SD = Results in Persistent or Significant Disability/Incapacity; SE = Serious Event; TEAE = Treatment-Emergent Adverse Event

T:\Medgenics\NFC-1\ADHD-201\...\xxx.sas run on DDMMMYYYY at HH:MM on data extracted on DDMMMYYYY

Listing 16.2.6.2 Serious Adverse Events Safety Population

{Similar shell as Listing 16.2.6.1, remove Any AEs column}

Listing 16.2.6.3
Adverse Events leading to Early Termination
Safety Population

{Similar shell as Listing 16.2.6.1, remove Any AEs column}

Listing 16.2.6.4 Listing of Deaths All Subjects

{Similar shell as Listing 16.2.6.1, remove Any AEs column}

Protocol: MDGN-NFC1-ADHD-201

Page 1 of x Final

Listing 16.2.7.1 Clinical Laboratory Data: Chemistry Safety Population

Treatment: XXXXXX

Subject ID	Laboratory Test (unit)	Visit	Collection Date	Test Result	Reference Range Low	Reference Range High	Flag [1]
		g .					**
XXXXXXXX	XXXXXXXXXXXX	Screening	DDMMMYYYY	XX.XX	XXX	XXX	Н
		Baseline	DDMMMYYYY	XX.XX	XXX	XXX	
		Visit 3	DDMMMYYYY	XX.XX	XXX	XXX	P; L
		Visit 4	DDMMMYYYY	XX.XX	XXX	XXX	
		Visit 5	DDMMMYYYY	XX.XX	XXX	XXX	
		Visit 6	DDMMMYYYY	XX.XX	XXX	XXX	L
		Visit 7	DDMMMYYYY	XX.XX	XXX	XXX	
		Visit 8/ET	DDMMMYYYY	XX.XX	XXX	XXX	
	xxxxxxxxxxxx	Screening	DDMMMYYYY	XX.XX	XXX	XXX	P
		Baseline	DDMMMYYYY	XX.XX	XXX	XXX	
		Visit 3	DDMMMYYYY	XX.XX	XXX	XXX	
		Visit 4	DDMMMYYYY	XX.XX	XXX	XXX	P; H
		Visit 5	DDMMMYYYY	XX.XX	xxx	XXX	
		Visit 6	DDMMMYYYY	XX.XX	xxx	XXX	Н
		Visit 7	DDMMMYYYY	XX.XX	XXX	XXX	Н
		Visit 8/ET	DDMMMYYYY	XX.XX	XXX	XXX	

{Repeat for all scheduled analytes}

^[1] H = High, L = Low, P = Potential Clinical Importance.

T:\Medgenics\NFC-1\ADHD-201\...\xxx.sas run on DDMMMYYYY at HH:MM on data extracted on DDMMMYYYY

Listing 16.2.7.2 Clinical Laboratory Data: Hematology Safety Population

{Similar shell as Listing 16.2.7.1}

Listing 16.2.7.3 Clinical Laboratory Data: Urinalysis Safety Population

{Similar shell as Listing 16.2.7.1}

Listing 16.2.7.4 Pregnancy Tests Safety Population

{Similar shell as Listing 16.2.7.1, limit to only female subjects, remove flag column}

Listing 16.2.7.5 Urine Drug Screen Safety Population

{Similar shell as Listing 16.2.7.1, remove reference limit columns and flag column}

Protocol: MDGN-NFC1-ADHD-201

Page 1 of x Final

Listing 16.2.8 Vital Signs Safety Population

Treatment: XXXXXX

Subject ID	Visit	Vital Signs Collected?	Date of Measurement	Height (cm)	Weight (kg)	Heart Rate (beats/min)	Respiratory Rate (breaths/min)	Systolic Blood Pressure (mmHg)	Diastolic Blood Pressure (mmHg)	BMI (kg/m^2)
xxxxxxxx	Screening	Yes	DDMMYYYY	XX X	XX.X	XXX	XXX	XX	XX	XX X
λλλλλλλ	Baseline	Yes	DDMMYYYY	XX X	XX.X	XXX	XXX	XX	XX	XX X
	Visit 3	Yes	DDMMYYYY	XX X	XX X*	XXX	XXX	XX	XX	XX X
	Visit 4	Yes	DDMMYYYY	XX X	XX.X	XXX	XXX	XX	XX	XX X
	Visit 5	Yes	DDMMYYYY	XX.X	XX.X	XXX	XXX^	XX	XX	XX X
	Visit 6	Yes	DDMMYYYY	XX X	XX.X	XXX	XXX	XX	XX*	XX X
	Visit 7	Yes	DDMMYYYY	XX X	XX.X	XXX	XXX	XX	XX	XX X
	Visit 8/ET	Yes	DDMMYYYY	XX X	XX.X	XXX	XXX	XX	XX	xx x^
xxxxxxx	Screening	Yes	DDMMYYYY	XX X	xx.x	xxx*#	XXX	XX	XX	XX X
	Baseline	Yes	DDMMYYYY	XX X	xx x^#	XXX	XXX	XX	XX	XX X
	Visit 3	Yes	DDMMYYYY	XX X	XX.X	XXX	XXX	XX	XX	XX X
	Visit 4	Yes	DDMMYYYY	XX X	XX.X	XXX	xxx*	XX	XX	XX X
	Visit 5	Yes	DDMMYYYY	XX X	XX.X	XXX	XXX	XX	XX	XX X
	Visit 6	Yes	DDMMYYYY	XX X	XX.X	XXX	XXX	XX	XX	xx x^
	Visit 7	Yes	DDMMYYYY	XX X	XX.X	xxx*	XXX	XX	XX	XX X
	Visit 8/ET	Yes	DDMMYYYY	XX X	XX.X	XXX	XXX	XX	XX	XX X

Note: * = High, ^ = Low, # = Potential Clinical Significance.

T:\Medgenics\NFC-1\ADHD-201\...\xxx.sas run on DDMMMYYYY at HH:MM on data extracted on DDMMMYYYY

Protocol: MDGN-NFC1-ADHD-201

Page 1 of x Final

Listing 16.2.9 Electrocardiograms (ECGs), Site Interpretation Safety Population

Treatment: XXXXXX

Subject ID	Visit	ECG Collected?	Datetime of Measurement	Investigator Interpretation
xxxxxxxx	Screening	Yes	DDMMYYYY:HH:MM	Normal
	Baseline	Yes	DDMMYYYY:HH:MM	Normal
	Visit 3	Yes	DDMMYYYY:HH:MM	Normal
	Visit 4	Yes	DDMMYYYY:HH:MM	Abnormal – Not clinically significant
